3.1.3. Patient's Global Impression of Change

The self-report measure Patient's Global Impression of Change (PGIC) reflects a patient's belief about the efficacy of treatment. It is a 7-point scale depicting a patient's rating of overall improvement. Patients rate their change as "very much improved," "much improved," "minimally improved," "no change," "minimally worse," "much worse," or "very much worse".

3.1.4. Clinical Global Impression-Severity of Symptoms Scale

The Clinical Global Impression-Severity of Symptoms Scale (CGI-S) is an observer-rated scale that will be used to measure symptom severity. It is important to note that the observer or rater will provide their assessment of the subject's symptoms at the time of the current visit.

To perform this assessment, the investigator (or designee) will answer the following question: "Considering your total clinical experience with this particular population, how ill is the subject at this time?" Response choices are 0 = not assessed; 1 = normal, not at all ill; 2 = borderline ill; 3 = mildly ill; 4 = moderately ill; 5 = markedly ill; 6 = severely ill; and 7 = among the most extremely ill subjects.

3.2. Safety Assessments

3.2.1. Adverse Event (AE)

An adverse event is any untoward medical occurrence in a patient or clinical trial subject, temporally associated with the use of trial treatment, whether or not considered related to the trial treatment.

An AE can therefore be any unfavorable and unintended sign (including an abnormal laboratory finding), symptom, or disease (new or exacerbated) temporally associated with the use of trial treatment. All adverse events will be recorded on the ADVERSE EVENTS eCRF.

3.2.1.1. Adverse Event of Special Interest (AESI)

AESIs will be captured and monitored during this study. AESI include AEs potentially related to abuse or dependence, AEs involving medical handling irregularities, hematologic abnormalities and abnormal liver function tests. These events will be noted by the investigator in the ADVERSE EVENTS CRF.

3.2.1.2. Pre-Treatment Adverse Event

Any recorded Adverse Event that occurs after obtaining informed consent but prior to the start of IMP.

3.2.1.3. Treatment-emergent Adverse Event (TEAE)

Any event reported on the CRF that occurs on or after the initiation of IMP through the last follow up contact is considered treatment emergent. Additionally, it is assumed that an AE which was reported to have started on Day 1 without an associated onset time is assumed to be treatment emergent.

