#### **Statistical Methods**

**Sample Size Estimation:** The sample size is not based on statistical power considerations. The trial population will be derived from eligible subjects from the double-blind, proof-of-concept Trial CVL-865-SZ-001. - Approximately 120 subjects are expected to complete Trial CVL-865-SZ-001 and be eligible for enrollment in CVL-865-SZ-002.

**Safety Analyses:** The safety analysis will be conducted on the Safety Set. The primary safety analysis is the frequency and severity of adverse events (AEs) during the Treatment Period. All AEs will be coded according to the Medical Dictionary for Regulatory Activities (MedDRA) preferred term. The incidence of treatment-emergent AEs (TEAEs) will include the following summaries:

- TEAEs by severity
- Drug-related TEAEs

[figure not shown]
- TEAEs with an outcome of death
- Serious TEAEs
- Discontinuations due to TEAEs
- TEAEs potentially related to abuse as assessed through the active monitoring of adverse events related to potential abuse and AEs involving medication handling irregularities

A TEAE for this study is defined as an AE that started after the first dose of IMP in the open-label trial or a previously reported AE that increased in intensity, became serious, trial drug-related, or resulted in death, discontinuation, interruption, or reduction of IMP after the first dose of IMP in the open-label trial.

Other safety endpoints, including clinical laboratory assessments, vital sign measurements, ECGs, medication withdrawal symptoms assessed by the Modified Clinical Institute Withdrawal Assessment – Benzodiazepines total scores at the scheduled visits, and suicidality monitored during the trial using the Columbia-Suicide Severity Rating Scale, will be summarized with descriptive statistics. Baseline is defined as the last assessment prior to the initiation of IMP in CVL-865-SZ-002. Additional presentations may be conducted evaluating changes from the original trial baseline. These analyses will be detailed in the statistical analysis plan.

Exploratory Analyses: Descriptive statistics will be provided for each efficacy endpoint and will be summarized at each trial visit using available data. Baseline is defined as the last assessment prior to the initiation of IMP in CVL-865-SZ-002. Additional presentations may be conducted evaluating changes from the original trial baseline. These analyses will be detailed in the statistical analysis plan.

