Laboratory														
Safety laboratory blood sample	X		X		X	X	X	X	X	X	X	X	X	X
Safety laboratory urine sample	X		X		X		X			X			X	
Urine pregnancy test h	X		X		X	X	X	X	X	X	X	X	X	X

Trial Period/ Phases	Double-blind Titration Phase (2 weeks)		Maintenance Phase (52 weeks) Visits 2 through 12											
	Visit 1/BL b,c	Contact	Visit 2	Contact	Visit 3 d	Visit 4 d	Visit 5 d	Visit 6 d	Visit 7 d	Visit 8 d	Visit 9 d	Visit 10 d	Visit 11 d	Visit 12 d
Visit/Contact a	1	8	15	29	43	71	99	127	155	183	211	239	267	295
Day	0	1	2	4	6	10	14	18	22	26	30	34	38	42
Week	± 3 days													
Window														
Urine drug screening i	X													
Blood sample for PK of CVL-865 j	X						X			X			X	
Blood sample for PK of AEDs k	X						X			X			X	
Other														
IMP dispensing	X		X		X		X			X			X	
IMP compliance assessment	X	X	X	X	X	X	X	X	X	X	X	X	X	X
AED compliance assessment	X	X	X	X	X	X	X	X	X	X	X	X	X	X

Abbreviations: AED = antiepileptic drug; BL = baseline; BZD = benzodiazepine; CGI-S = Clinical Global Impression – Severity; C-SSRS = Columbia-Suicide Severity Rating Scale; ECG = electrocardiogram; ICF = informed consent form; IMP = investigational medicinal product; PGI-C = Patient Global Impression of Change; PK = pharmacokinetics.

- a. Contact with subject via phone call, internet/web, or other acceptable means of communication to check on their status.
- b. Screening/Baseline for Trial CVL-865-SZ-002 occurs at Visit 1, which is the same day as Visit 4 in Trial CVL-865-SZ-001. Any assessments conducted for Visit 4 of Trial CVL-865-SZ-001 will be considered the baseline assessments for Visit 1 of Trial CVL-865-SZ-002.
- c. Individual sites may require subjects to have COVID-19 testing done prior to enrollment. COVID-19 testing may be performed after enrollment per the investigator's discretion.
- d. In the event that a subject is unable to attend a clinic visit in person due to restrictions related to COVID-19, this visit may be completed remotely. Please refer to the Trial Operations Manual for further instructions related to remote visits.

- e. The physical examination should include weight at all time points. Physical and/or neurological examinations can be done at any time point during the trial at the investigator's discretion.

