#### **9.4.1 Safety Analyses**

The safety analysis will be conducted on the Safety Set. The primary safety analysis is the frequency and severity of AEs during the Treatment Period. All AEs will be coded according to MedDRA preferred term. The incidence of treatment-emergent AEs (TEAEs) will include the following summaries:

- TEAEs by severity
- Drug-related TEAEs
- TEAEs with an outcome of death
- Serious TEAEs
- Discontinuations due to TEAEs

- TEAEs potentially related to abuse as assessed through the active monitoring of adverse events related to potential abuse and adverse events involving MHI

A TEAE is defined as an AE that started after the first dose of IMP in the open-label trial or a previously reported AE that increased in intensity, became serious, trial drug-related, or resulted in death, discontinuation, interruption, or reduction of IMP after the first dose of IMP in the open-label trial.

Other safety endpoints, including laboratory assessments, vital sign measurements, ECGs, medication withdrawal symptoms assessed by the mCIWA-B total scores at the scheduled visits and suicidality monitored during the trial using C-SSRS, will be summarized with descriptive statistics. Baseline is defined as the last assessment prior to the initiation of IMP in CVL-865-SZ-002. Additional presentations may be conducted evaluating changes from the original trial baseline. These analyses will be detailed in the statistical analysis plan.

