**Table 13 Follow-Up of AEs and SAEs**

Follow-Up of AEs and SAEs

 
The investigator is obligated to perform or arrange for the conduct of supplemental measurements and/or evaluations as medically indicated or as requested by the sponsor or designee to elucidate the nature and/or causality of the AE or SAE as fully as possible. This may include additional laboratory tests or investigations, histopathological examinations, or consultation with other health care professionals.
 
If a subject dies during participation in the trial or during a recognized follow-up period, the investigator will provide the sponsor or designee with a copy of any post-mortem findings including histopathology.
 
New or updated information will be recorded in the originally completed eCRF.
 
The investigator will submit any updated SAE data to the sponsor or designee within 24 hours of receipt of the information.
 

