4.1.21. Handling of Missing Severity or Relationship for Adverse Events

Adverse events with missing severity will have the severity imputed as 'Severe'. Adverse events with missing relationship to CVL-865 will have the relationship imputed as 'Related' if the AE started after the first CVL-865 dose in CVL-865-SZ-002.

Actual values will be presented in the data listings.

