5.12.1. Adverse Events

Adverse events will be mapped to a Medical Dictionary for Regulatory Activities (MedDRA) version 27.1 or higher PT and SOC. If a subject experiences multiple events that map to a single PT, the greatest intensity and strongest investigator assessment of relation to IMP will be assigned to the PT for the appropriate summaries. Events with missing intensity or relationship will be classified as outlined in [Section 4.1.21](#). Summaries of TEAEs will include any AEs reported beginning with the initiation of study drug on Day 1 through last follow up contact. The occurrence of TEAEs will be summarized by PTs, SOCs, and intensity. Separate summaries of treatment-emergent serious adverse events (TESAEs), TEAEs related to IMP, TEAEs leading to death, AESIs (including those potentially related to abuse as assessed through the active monitoring of adverse events related to potential abuse and AEs involving medication handling

irregularities), AESIs not leading to discontinuation of IMP, TEAEs leading to the discontinuation if IMP and events leading to discontinuation of study will be generated respectively. A presentation of AEs by dose at event onset will be prepared. All adverse events reported will be listed for individual subjects showing both verbatim and PTs. All adverse events that occurred prior to the initiation of study will be excluded from the tables but will be included in the listings.

Missing onset dates will be imputed as previously outlined in [Section 4.1.22](#) as required to determine TEAEs.

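### The SAP drops the second half of the protocol's TEAE definition (earlier AEs that worsen or change status on open-label drug) without declaring a change

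*SAP*

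**What the plan says.** The protocol defines a TEAE in two places, the Synopsis (Statistical Methods) and Section 9.4.1, to the same effect. The first part is new onset: "A TEAE for this study is defined as an AE that started after the first dose of IMP in the open-label trial". The second part, joined by 'or', is "a previously reported AE that increased in intensity, became serious, trial drug-related, or resulted in death, discontinuation, interruption, or reduction of IMP", where the change follows the first open-label dose.

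SAP 3.2.1.3 keeps only a timing rule. An event that "occurs on or after the initiation of IMP through the last follow up contact is considered treatment emergent", and a Day 1 onset with no recorded time is also counted. SAP 5.12.1 repeats the timing rule for the summaries and adds: "All adverse events that occurred prior to the initiation of study will be excluded from the tables but will be included in the listings". It makes no exception for an earlier event that later changes. SAP Section 6 speaks only of future departures from the SAP, and the revision history in Section 7 has no entries.

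**The concern.** TEAEs, serious and non-serious, head the list of primary endpoints in both documents. This is a rollover trial: "Screening/Baseline for Trial CVL-865-SZ-002 occurs at Visit 1, which is the same day as Visit 4 in Trial CVL-865-SZ-001". Subjects may therefore start open-label drug with AEs from the double-blind trial still ongoing. Those who had been on placebo or 7.5 mg BID are titrated to 25 mg BID over two weeks (Protocol Table 4). An existing AE that worsens or changes status under open-label drug is what the protocol's second part is meant to count.

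Without it, such an event can be absent from the overall, serious, related, fatal and leading-to-discontinuation TEAE tables. Dropping the second part can only lower those counts. The resulting tables would not meet the protocol's definition, and nothing would tell the reader so.

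**Working it through.** The plan states no figure on this point, so the check is a comparison of text.

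**Step 1. Does the SAP's word 'occurs' cover a later change in an existing AE?** The surrounding rules indicate that onset is meant:
- The Day 1 sentence in SAP 3.2.1.3 concerns when an AE started.
- SAP 5.12.1 imputes missing onset dates in order to decide which AEs are TEAEs.
- The exclusion sentence in 5.12.1 sends earlier events to the listings only.
- SAP 4.1.21 imputes a missing relationship as related only "if the AE started after the first CVL-865 dose in CVL-865-SZ-002".
- SAP 4.1.22 ties emergence to the start date in its rule for missing end dates. This is consistent with the onset reading but does not prove it alone.
- SAP 3.2.1.2 classes an event between consent and first dose as pre-treatment and gives no way to reclassify it.

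A programmer working from this text would derive TEAEs from the onset date.

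**Step 2. Each protocol trigger against its route into the SAP tables.**

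| Protocol trigger after first open-label dose | Route into the SAP's TEAE tables |
|---|---|
| New onset | Counted; slightly wider than the protocol, because Day 1 onsets without a time are included |
| Earlier AE worsens | Only if the site enters the exacerbation as a new AE (Protocol Table 10 and SAP 3.2.1 allow this) |
| Earlier AE becomes serious | None, unless re-recorded |
| Earlier AE becomes drug-related | None, unless re-recorded; Protocol 10.3.3 lets the investigator revise causality during follow-up |
| Earlier AE results in death | None, unless re-recorded |
| Earlier AE leads to discontinuation, interruption or reduction of IMP | None, unless re-recorded |

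In the last row, SAP 5.12.1 plans no separate table for AEs leading to interruption or reduction. An earlier AE behind a dose reduction could therefore appear in the listings only.

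**Step 3. Would re-recording close the gap?** Protocol Table 13 points the other way: "New or updated information will be recorded in the originally completed eCRF". An update to an existing record need not create a new onset date.

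**Step 4. Size.** The only usable input is the roughly 120 subjects expected (Protocol 9.2, SAP 1.2). One subject missing from a row lowers its incidence by 1/120 = 0.0083, or 0.83 percentage points. This holds for an all-subjects column and for a subject with no other qualifying event in that row. Columns by SZ-001 treatment group (SAP 5.1) have smaller denominators, so the shift there would be larger. The documents give no count of AEs ongoing at rollover, so a total cannot be computed.

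**The case against.** The mismatch in wording is not in dispute. The case on the other side concerns its consequences.

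- **Carry-over is not described.** The instruction in Table 13 governs records in this trial, while the original record of an SZ-001 AE belongs to another trial. Ongoing SZ-001 AEs might be entered as medical history at Visit 1. A worsening would then be an exacerbation with a new onset, and already counted. This stands as a possibility, and it makes the use of Table 13 for carried-over AEs an assumption. At most it covers worsening. It does not cover an AE that only changes in seriousness, causality or effect on dosing.
- **Part of the loss is captured elsewhere.** The events stay in the listings. Laboratory abnormalities are analysed from the values (SAP 3.2.2.1, 5.12.4). AESI summaries and events leading to study discontinuation (5.12.1) may hold some, as may discontinuation reasons (5.7, 5.8). Some partial or missing start dates are imputed to Day 1 (4.1.22), which would bring some carried-over AEs into the tables. All of this stands, and it makes the loss partial.
- **The trial is descriptive and the effect may be small.** This is true and limits the severity. It does not make the tables conform to the protocol.
- **A full repair depends on the data.** The documents do not show that the date on which an AE became serious or related is captured. The EXPOSURE CRF holds dosing data but is not shown to say which AE led to a dose change. This stands and is why the fix needs a fallback.

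**Conclusion.** The concern holds. The SAP's TEAE definition is narrower than the protocol's on a primary endpoint, and the change is not declared. The textual finding is firm. It rests on reading 'occurs' as onset, which the linked SAP rules support.

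The practical effect is uncertain. It depends on how many SZ-001 AEs were ongoing at rollover and on how sites recorded later changes, and the documents give neither. The effect may be small. This should be fixed before database lock; it does not threaten the trial.

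**What to change.** **Core change.** In SAP 3.2.1.3 and 5.12.1, keep the present text, including the Day 1 rule and the end point at the final follow-up contact. Add that a previously reported AE is also treatment-emergent if it meets any of the protocol's second-part triggers after the first SZ-002 dose and up to that end point. Exempt such AEs from the exclusion sentence in 5.12.1.

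**Linked rules.**
- In 4.1.22, allow emergence through the second part as well as through the start date.
- In 4.1.21, say how a missing relationship is handled for a second-part AE, and that an imputed severity or relationship is not in itself a trigger.
- State how AEs ongoing at rollover are identified (for example, SZ-001 records with no end date, or an end date on or after extension Day 1) and linked to SZ-002 records.
- SAP 5.12.1 says "A presentation of AEs by dose at event onset will be prepared". For second-part events, use the date of the qualifying change there and in any display by time. For action on IMP, the EXPOSURE CRF may supply that date, but the link to the AE must come from the AE record.

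**Fallback.** If the records do not support a trigger or its date, name which one and declare the narrower definition in SAP Section 6 as a change from the protocol.

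**Cost.** The wording edits are small. The main work is linking AE records across the two trials, and how complete that can be depends on how SZ-001 AEs were recorded. No extra subjects, visits or tables are needed. TEAE counts may rise slightly.

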3.2.2. Clinical Safety Laboratory Assessments

The clinical laboratory tests as listed in the protocol will be performed in accordance with the laboratory manual and the Schedule of Assessments. All results, including repeats, will be included in the laboratory reports. The investigator must review the laboratory report, document this review, and record any clinically relevant changes occurring during the trial in the AE section of the eCRF.

3.2.2.1. Treatment-emergent Laboratory Abnormality

A treatment-emergent laboratory abnormality is defined as value outside the normal range which occurs on or after the start of IMP through the last follow up contact. Where applicable, these abnormalities will be graded.

3.2.3. Columbia-Suicide Severity Rating Scale (C-SSRS)

Suicidality will be monitored during the trial using the C-SSRS. It was designed to quantify the severity of suicidal ideation and behavior.

The “Since Last Visit” C-SSRS form will be completed at all visits. The investigator will review the results of the “Since Last Visit” C-SSRS during the trial to determine whether it is safe for the subject to continue in the trial. If a subject demonstrates potential suicidal ideation associated with actual intent or method or plan as indicated by “YES” answers on item 4 or 5 of the C-SSRS, the investigator will need to evaluate whether a risk assessment by a qualified mental health professional (MHP, or the investigator alone if the investigator is a qualified MHP) is needed and whether the subject should continue in the trial or be discontinued. Baseline values for C-SSRS will come from study CVL-865-SZ-001.

Details of C-SSR categories are provided in [Section 9.2](#).

3.2.4. Modified Clinical Institute Withdrawal Assessment – Benzodiazepines (mCIWA-B)

The modified Clinical Institute Withdrawal Assessment Scale – Benzodiazepines (mCIWA-B) is a sensitive instrument to measure withdrawal under conditions where there is a taper of medication (rather than abrupt discontinuation). It consists of 17 items that monitor the type and severity of benzodiazepine withdrawal symptoms such as irritability, fatigue, appetite, and sleeplessness ([Busto et al, 1989](#)). The clinician-observed assessments of sweating, restlessness (pacing), and tremor that are included in the overall version have been removed from this modified version. The total score ranges from 1 to 68 with higher scores indicating more severe withdrawal.

3.2.5. Vital Signs

Vital sign measurements will include body temperature, respiratory rate, systolic blood pressure, diastolic blood pressure, and heart rate.

Vital signs will be measured with the subject in a sitting/semi-recumbent position after 5 minutes rest and will include temperature, systolic and diastolic blood pressure, and heart rate.

A properly sized and calibrated blood pressure cuff will be used to measure blood pressure each time. The use of an automated device for measuring blood pressure and heart rate is acceptable, although, when done manually, heart rate will be measured in the brachial/radial artery for at least 30 seconds. When the timing of these measurements coincides with a blood collection, blood pressure and heart rate should be obtained prior to the nominal time of the blood collection.

Body temperature will be measured with either an oral (temperature taken at floor of the mouth) or tympanic thermometer. The same method (ie, oral or tympanic) must be used for all measurements for each individual subject and should be the same for all subjects.

3.2.6. Electrocardiograms

Electrocardiogram (ECG) recordings will be obtained after the subject has been at rest for at least 5 minutes. Additional 12-lead ECGs may be obtained at the investigator's discretion and should always be obtained in the event of early termination. The ECG results will be evaluated at the investigational site to determine the subject's eligibility and to monitor safety during the trial. The investigator (or qualified designee) will review, sign, and date each ECG reading, noting whether or not any abnormal results are of clinical significance. Any clinically relevant changes occurring during the trial will be recorded in the AE section of the eCRF. The ECG will be repeated if any results are considered to be clinically significant. A central ECG service will be used for reading all ECGs in order to standardize interpretations for the safety analysis.

